8.1.6. Analysis based on the person-years method

The incidence rate per exposure period will be calculated using the following formula:

$$\text{Incidence rate (per 100 person-years)} = 100 * y / PT$$

y: Number of patients with event

PT: Total exposure period (years)

Where the exposure period is the period from the first date of administration to the date of last observation in this study for patients with no event and the period from the first date of administration to the first date

of confirmation of the event in this study for patients with an event. The 95% confidence interval will be calculated using the following formula:

$$\left[\frac{100}{PT} \cdot \frac{1}{2} \chi^2_{2y} \left(\frac{\alpha}{2} \right), \frac{100}{PT} \cdot \frac{1}{2} \chi^2_{2(y+1)} \left(1 - \frac{\alpha}{2} \right) \right]$$

y: Number of events

$\chi^2_{2y}(\alpha/2)$: $\alpha/2$ percent point of the chi-square distribution with $2y$ degrees of freedom

8.2. Statistical Analysis

The analyses to be performed on the safety analysis set or the efficacy analysis set, shown below, will also be performed on the safety analysis set consisting of consented patients or the efficacy analysis set consisting of consented patients. Applicable analyses will be specified separately. When these analyses are performed, the analysis populations will be replaced with the safety analysis set consisting of consented patients or the efficacy analysis set consisting of consented patients.

8.2.1. Overview of patients

8.2.1.1. Patient disposition

For patients with collected case report forms, the number of patients completing the study, the number of patients in the safety analysis set, and the number of patients in the efficacy analysis set will be tabulated. In addition, the numbers of patients excluded from the safety analysis set and the efficacy analysis set and the number of patients by reason for exclusion will be tabulated.

8.2.1.2. List of discontinuations and dropouts

For the safety analysis set and the efficacy analysis set, the number and proportion of discontinuations will be tabulated by timing [<12 months, ≥ 12 to <24 months, ≥ 24 to <30 months, ≥ 30 months]. In addition, the number and proportion of patients by reason for discontinuation will be tabulated.

8.2.1.3. List of excluded patients by patient

A listing of patients excluded from the safety analysis, patients excluded from the efficacy analysis, and reasons for exclusion will be prepared.

8.2.2. Patient characteristics and history of treatment

8.2.2.1. Patient characteristics

For the safety analysis set and the efficacy analysis set, the following patient characteristics will be tabulated as described in Section 8.1:

- Target disease [ATTR-CM, others]
- Gender [male, female]

- Age (continuous variable)
- Age [<15 years, ≥15 to <65 years, ≥65 years]
- Inpatient/outpatient status at the first prescription [inpatient, outpatient]
- Body height (continuous variable)
- Body weight (continuous variable)
- BMI [<18.5, ≥18.5 to <25, ≥25]
- TTR genotype [wild-type, variant, unknown]
- NYHA functional classification [Class I, II, III, IV]
- mBMI (continuous variable, see Section 11.3 for the calculation method)
- Severity of liver impairment [mild, moderate, severe, unknown]
- Liver impairment [absent, present, unknown]
- Renal impairment [absent, present, unknown]
- Complication [absent, present]
- Usage experience of this drug (administered this drug for the first time, transferred from clinical trials, transition from the treatment of ATTR-PN, no information)
- Pregnancy status [absent, present]
- Concomitant drug therapy [absent, present]
- Concomitant non-drug therapy (device therapy) [absent, present]

For the safety analysis set, the number and proportion of the following patients will be tabulated by System Organ Class (SOC) and Preferred Term (PT):

- Breakdown of complications

For the safety analysis set, the number and proportion of patients for each of the following breakdowns will be tabulated:

- Breakdown of concomitant medications (Concomitant medications are defined as drugs used between the start date of administration of this drug and the date of discontinuation or end date of administration of this drug among those entered in the drug therapy section of the case report form.)
- Breakdown of concomitant non-drug therapies (device therapies) (Concomitant non-drug therapies are defined as non-drug therapies (device therapies) performed between the start date of administration of

this drug and the date of discontinuation or end date of administration of this drug among those entered in the non-drug therapy (device therapy) section of the case report form.)

- The classification of device therapies (pacemaker, implantable cardioverter defibrillator [ICD], cardiac synchronization therapy [CRTP], biventricular pacing implantable cardioverter defibrillator [CRTD], other) will be tabulated. Other breakdowns will be listed.
- Breakdown of TTR genotypes (variant only)

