### **8.3.3. Concomitant therapy**

#### **8.3.3.1. Drug therapy**

For all drugs used during observation period, the following information should be recorded.

1. Drug name
2. Route of administration
3. Start date (the date entry is not necessary if the drug has been administered before the start of the study)
4. End date
5. Purpose of administration (for treatment of ATTR-CM, procedure for adverse events, or others)

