##### 2. Method of analysis

- Analysis for safety evaluation

Events possibly related to this drug are considered as adverse drug reactions (ADRs). The number of patients with ADRs and the proportion  $[(\%): \text{number of patients with ADRs} / \text{number of patients included in the SAS}]$  will be calculated.

Based on the above method, important missing information and important potential risks will also be evaluated.

- Analysis for effectiveness evaluation

Time course of changes in the following items from the start of administration of this drug will be recognized.

- NYHA Functional Classification
- Cardiac biomarker values (NT-pro BNP, BNP, troponin I, and troponin T)

In addition, survival time analysis will be performed using survival information obtained up to 30 months after the start of administration.

- Subset analysis

The analysis by variant genotype and NYHA Functional Classification will be also performed for the above safety and effectiveness evaluations.

Also, the onset status of adverse reactions will be evaluated for each product (Vyndaqel or Vynmac) during the treatment period until the first switching to Vynmac for Vyndaqel and during the treatment period after the first switching to Vynmac for Vynmac.

Detailed methodology for summary and statistical analyses of data collected in this study will be documented in the SAP, which will be dated, filed and maintained by the Sponsor. The SAP may modify the plans outlined in the full protocol; any major modifications of primary endpoint definitions or their analyses would be reflected in a full protocol amendment.

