5.4. Subgroups

Subgroup analyses of safety will be performed for the following patient characteristics and other factors. For the patient characteristics and other factors with those of specific categories underlined, a risk ratio will be calculated using each underlined category as the reference.

- Inpatient/outpatient status at the first prescription [inpatient, outpatient]
- *Severity of liver impairment [absent, mild, moderate, severe]
- Liver impairment [absent, present]
- Renal impairment [absent, present]
- Age [<15 years, ≥15 to <65 years, ≥65 years]
- *TTR genetic variant [wild-type, variant]
- NYHA functional classification [Class I/II, III/IV]
- NYHA functional classification [Class I, II, III, IV]
- Concomitant medication [absent, present]
- Non-drug therapy (device therapy) [absent, present]

- Complication [absent, present]
- Gender [male, female]
- Usage experience of this drug (administered this drug for the first time, transferred from clinical trials, transition from the treatment of ATTR-PN)

*Evaluation of the important missing information (safety in patients with severe liver impairment and patients with variants)

Subgroup analyses of efficacy will be performed for the following patient characteristics:

- TTR genetic variant [wild-type, variant]
- NYHA functional classification [Class I/II, III/IV]
- NYHA functional classification [Class I, II, III, IV]

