8.2.3.3. Exploratory analysis

For each of the factors specified in Section 5.4, the number and proportion of patients with at least one adverse reaction (incidence of any type of adverse reactions) will be tabulated, and for the incidence, the risk ratio among subgroups for each factor will be calculated as described in Section 8.1.3. However, after reconsidering the classification of a category with <10 patients, if calculation of a risk ratio is difficult, the

risk ratio to the category will not be calculated. In addition, unknown data will be excluded from the evaluation of risk ratios.

Serious adverse reactions and serious adverse events will also be analyzed in the same manner as above.

Adverse reactions will be tabulated by SOC and PT for each of the following subgroups:

- Liver impairment [absent, present]
- Renal impairment [absent, present]
- Age [<15 years, ≥15 to <65 years, ≥65 years]
- Pregnancy status [absent, present]
- NYHA functional classification [Class I, II, III, IV]

The onset status of adverse reactions will be evaluated for each product (Vyndaqel or Vynmac) during the treatment period until the first switching to Vynmac for Vyndaqel and during the treatment period after the first switching to Vynmac for Vynmac.

This drug is contraindicated to patients with a history of hypersensitivity to any of its ingredients. Because of limitations in evaluation in this study, no tabulation regarding contraindications will be performed. However, if hypersensitivity to any of its ingredients is reported as an adverse reaction, it will be presented in a listing.

Additional analyses may be performed as necessary. The exploratory analysis will be reported only when results giving important interpretation are obtained.

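### As defined, the concomitant-medication and device-therapy safety subgroups can include therapy started because of the event, which biases their risk ratios above 1

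*SAP*

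**What the plan says.** SAP 5.4 lists the safety subgroup factors. Two of them are "Concomitant medication [absent, present"] and "Non-drug therapy (device therapy) [absent, present"]. Neither carries a condition on timing or purpose.

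SAP 8.2.3.3 calculates a risk ratio for the incidence of any adverse reaction for each factor in 5.4, and repeats this for serious adverse reactions and serious adverse events.

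The only definitions are in SAP 8.2.2.1, next to the breakdown tables: "Concomitant medications are defined as drugs used between the start date of administration of this drug and the date of discontinuation" or the end of administration, and "Concomitant non-drug therapies are defined as non-drug therapies (device therapies) performed between the start date of administration of" this drug and the same end point. Neither requires the therapy to precede the event or excludes therapy given for it.

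The data collected do include such therapy. Protocol 8.3.3.1 says "For all drugs used during observation period, the following information should be recorded", with a field "Purpose of administration (for treatment of ATTR-CM, procedure for adverse events, or others"). The SAP never uses that field. Protocol 8.3.3.2 records devices started during observation with a start date but no purpose.

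SAP 8.2.3.3 ends: "The exploratory analysis will be reported only when results giving important interpretation are obtained". The same sentence closes 8.2.4.4. Protocol 8.7 states "The analysis by variant genotype and NYHA Functional Classification will be also performed for the above safety and effectiveness evaluations", and also calls for evaluation of reactions by product and of the important missing information.

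**The concern.** A subgroup factor for a risk ratio should be fixed before the outcome can influence it. Here the outcome can set the factor. A patient on no other drug who has a reaction and is treated for it becomes present because of the reaction; without the reaction the same patient would have stayed absent. Events leave the absent group and enter the present group, so the ratio rises even if concomitant therapy has no effect on risk.

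The device factor is exposed in the same way, most clearly for serious adverse events of any cause. Protocol 10.4.1 counts progression of the underlying disease as an adverse event and 10.4.2 counts hospitalization as serious, so one admission that ends with an implanted device is both the outcome and the reason for being classed as present.

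The report could then show concomitant drugs or devices as a risk factor for reactions to this drug when the ratio reflects only treatment of the reactions. Separately, the closing sentence of 8.2.3.3 leaves unclear whether planned subgroup results, including variant status, severity of liver impairment and the by-product evaluation, are reported regardless of what they show.

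**Working it through.** **Plan's own figure.** The documents give none on this point. The probability of about 98% in Protocol 8.5.2 concerns hepatotoxicity counts. It reproduces (exact binomial, 300 patients, 5.88%, at least 10 cases: 0.984) but does not enter here.

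**Inputs.** N = 300 (Protocol 8.5.1). The other three are assumptions, because the documents give no values:
- c = share already using the therapy regardless of any event
- r = event risk, the same in everyone, so the true risk ratio is 1
- q = share of event patients otherwise without the therapy who start it because of the event

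**Formulas.**
- Risk if present = r[c + (1−c)q] / [c + (1−c)rq]
- Risk if absent = r(1−q) / (1−rq)

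**Medication, central case** (r = 15%, c = 80%, q = 50%).
- Present: 0.15 × (0.8 + 0.2 × 0.5) / (0.8 + 0.2 × 0.075) = 0.135 / 0.815 = 16.6%
- Absent: 0.15 × 0.5 / (1 − 0.075) = 0.075 / 0.925 = 8.1%
- Ratio: 2.04

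**Medication, range** (r 10–25%, c 70–90%, q 30–70%).
- Lowest, at r = 25%, c = 90%, q = 30%: 25.6% / 18.9% = 1.35
- Highest, at r = 10%, c = 70%, q = 70%: 12.6% / 3.2% = 3.9

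**Device, example** (r = 20%, c = 10%, q = 10%).
- Present: 0.2 × (0.1 + 0.9 × 0.1) / (0.1 + 0.9 × 0.02) = 0.038 / 0.118 = 32.2%
- Absent: 0.2 × 0.9 / (1 − 0.02) = 0.18 / 0.98 = 18.4%
- Ratio: 1.75

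**Precision at N = 300.** Wald 95% intervals at the expected counts; simulation of 20,000 runs, with at least 10 patients required per category.

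| Factor | c | r | q | Ratio | Expected patients in smaller group (events) | Interval | Runs with lower limit above 1 |
|---|---|---|---|---|---|---|---|
| Medication | 80% | 15% | 50% | 2.04 | 55.5 absent (4.5) | 0.81–5.2 | about 23% |
| Medication | 90% | 15% | 50% | 1.94 | 27.8 absent (2.3) | 0.54–7.0 | about 0.2% |
| Device | 10% | 20% | 10% | 1.75 | 35.4 present (11.4) | 1.02–3.0 | about 52% |
| Device | 20% | 20% | 10% | 1.41 | 64.8 present (16.8) | 0.86–2.3 | about 30% |
| Device, serious events | 20% | 50% | 10% | 1.23 | 72 present (42) | 0.97–1.56 | about 41% |

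At c = 98% for medication (same r and q as the first two rows) the absent group falls below 10 patients in about 95% of runs, and 8.2.3.3 would then usually give no ratio.

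**Check of the remedy.** With q = 0, which is what classification at the start of administration achieves, both formulas reduce to r and the expected ratio is 1.00 for every c and r.

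**The case against.** **The definition belongs to another table.** It is attached to the breakdown tables, and 5.4 has none of its own. This stands as a limit: carrying the window over to the subgroup is the natural reading but is not stated. If the sponsor intended another definition, it is nowhere written.

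**For medication the effect may not show.** Many of these patients probably take other drugs. If nearly all do, the absent group is tiny and the ratio is very imprecise or dropped under the rule for categories below 10 patients. This stands for medication. It does not rescue the device factor, where the smaller group is the present one.

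**The window closes at discontinuation or end of administration.** Therapy begun after stopping for a reaction is not counted, and early stoppers have less time to become present. This works the other way and is not in the model. It may offset part of the bias, by an amount the documents do not allow one to estimate.

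**The reporting sentence may be narrow.** It follows directly after the statement that additional analyses may be done, so it may cover only those. A reader might infer that the SAP would publish the spurious ratio and suppress reassuring results on variants and severe liver impairment. The documents do not support that. SAP 9 lists reactions in both groups with no condition on results, 8.2.2.1 tabulates how many patients are in each category, and Protocol 8.7 requires the evaluations. An important result also need not be a non-null one. What stands is the ambiguity: the section is itself titled as exploratory, and nothing limits the sentence to unplanned work.

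**Multiplicity.** A reader might also count the ratios implied by 5.4 and predict chance findings. That section ties ratios to factors with an underlined reference category, and the underlining is not visible in the text available, so no count is reliable. SAP 4 and 4.1 already treat tests as exploratory and p-values as descriptive.

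**Conclusion.** The point holds on the natural reading of the SAP. Any q above zero pushes the expected ratio above 1 in this model when concomitant therapy has no effect; only the size needs assumptions. Under those shown it is about 1.35 to 3.9 for medication, with wide intervals and possibly no ratio at all, and about 1.75 for devices in the example. All of these leave out the opposing effect of the window closing at discontinuation. The device factor is the firmer case. The analyses are labelled exploratory, which limits the consequence but does not remove the bias.

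On reporting, the supported conclusion is narrower: the sentence can be read to allow result-dependent reporting of planned subgroup analyses and should be clarified. The change should be made, but the study's main descriptive results do not depend on it.

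**What to change.** 1. In SAP 5.4 and 8.2.3.3, classify medication and device therapy for the risk ratios by what was in use at the start date of administration of this drug: recorded as begun before that date, or with a start date on or before it. Keep the on-treatment definition for the descriptive breakdown tables only. State how undated entries are treated, because Protocol 8.3.3 waives the date for therapy begun before the start of the study, which need not be the first dose and matters most for retrospectively included patients.
2. If that cannot be derived for drugs, excluding those coded as given for an adverse event is a fallback. It is not available for devices, which have a start date but no purpose field.
3. State that every analysis named in 8.2.3.3 and 8.2.4.4 is reported whatever its result, and that the restrictive sentence applies only to additional unplanned analyses.

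The cost is a few sentences in the SAP, a derived baseline indicator for each of the two factors from fields already on the case report form, and possibly some extra tables in the report. No new data are needed.

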8.2.2.2. Administration status of this drug

For the safety analysis set, the following administration status of this drug will be tabulated:

- For a patient receiving Vynmac, the dose of Vyndaqel will be used in the tabulation of doses; 61 mg of Vynmac will be considered equivalent to 80 mg of Vyndaqel. Treatment period (continuous variable, unit = month)
 1. Treatment period for any product
 2. Treatment period with Vyndaqel before the initial switching to Vynmac
 3. Treatment period with Vynmac after the initial switching to Vynmac
- Treatment period (categorical variable, [<12 months, ≥12 to <24 months, ≥24 to <30 months, ≥30 months])
 1. Treatment period for any product
 2. Treatment period with Vyndaqel before the initial switching to Vynmac
 3. Treatment period with Vynmac after the initial switching to Vynmac
- Initial dose (categorical variable, [20 mg, 40 mg, 60 mg, 80 mg]; for an initial dose >80 mg, a subcategory of >80 mg will be used.)
- Number of doses per actual treatment period (excluding the washout period from the treatment period) (total number of doses/actual treatment period [days]) (continuous variable)
- Dose per actual treatment period (excluding the washout period from the treatment period) (total dose/actual treatment period [days]) (continuous variable)
- Number and proportion of patients with dose reductions*

*Including a dose change from Vynmac 61 mg to Vyndaqel ≤60 mg.
- Number and proportion of patients with dose increases**

** Including a dose change from Vyndaqel ≤60 mg to Vynmac 61 mg.

- Breakdown of reduced doses (categorical variable)

The frequency and proportion will be tabulated for each dose pattern (maximum dose \Rightarrow minimum dose) during the observation period* [80 mg \Rightarrow 60 mg, 80 mg \Rightarrow 40 mg, 80 mg \Rightarrow 20 mg, 60 mg \Rightarrow 40 mg, 60 mg \Rightarrow 20 mg, 40 mg \Rightarrow 20 mg, no change].

Treatment period is defined as the period from the first date of administration to the last date of confirmation of administration in this study, including washout period.

If the treatment period overlaps between the administration records collected before and after transfer for a transferred patient, the patient will be handled as having received this drug at one of the sites if the number of doses per day and the administered dose during the overlapping period are the same. If there is any inconsistency in the number of doses per day or the administered dose during the overlapping period, the patient will not be included in the tabulation of the number of doses and the administered dose per actual treatment period or the dose increases and reductions, and the such action taken will be described in the report.

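### The breakdown of reduced doses pairs each patient's maximum and minimum dose without time order, so a dose that only rose is filed as a reduction

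*SAP*

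**What the plan says.** SAP 8.2.2.2 opens with the population for all its exposure tables: "For the safety analysis set, the following administration status of this drug will be tabulated". Four of its items matter here.

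- Starting dose: "Initial dose (categorical variable, [20 mg, 40 mg, 60 mg, 80 mg", with a further category above 80 mg. Starts below 80 mg are therefore provided for.
- Dose changes: one row counts patients with reductions and another counts patients with increases ("Number and proportion of patients with dose increases"). The note to the increase row reads "Including a dose change from Vyndaqel ≤60 mg to Vynmac 61 mg".
- Dose conversion: "61 mg of Vynmac will be considered equivalent to 80 mg of Vyndaqel".
- The table at issue, "Breakdown of reduced doses (categorical variable"): "The frequency and proportion will be tabulated for each dose pattern". The pattern runs from maximum dose to "minimum dose) during the observation period". The categories are the six descending pairs that can be formed from 80, 60, 40 and 20 mg, plus one for no change.

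**The concern.** The table's title promises reductions, but the rule beneath it uses two order-free quantities. A maximum and a minimum say how far apart a patient's doses were, not which came first. There is no ascending pair and no increase-only category, so a patient whose dose only rose has nowhere to go except a descending pair.

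The table would then mix upward and downward changes. A reader would take every descending pair as a fall in dose, and Protocol 8.2.1 quotes the Vyndaqel label as allowing a decrease when the dose is not tolerated. The table also sits beside a dose-reduction row with which it may not reconcile. Under SAP section 3 the final analysis supports the reexamination application, so the report would have to explain the difference.

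**Working it through.** The plan gives no figure to reproduce, because the point concerns a classification rule. The check applies the rule as written.

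**Inputs**, all from SAP 8.2.2.2: dose levels 20, 40, 60 and 80 mg; Vynmac 61 mg counted as 80 mg; category = maximum ⇒ minimum, or no change if the two are equal.

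**Comparator:** the largest fall from an earlier to a later dose.

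| Doses in time order (mg) | Filed under the SAP rule | Largest fall that occurred |
|---|---|---|
| 80 → 20 | 80 ⇒ 20 | 80 ⇒ 20 |
| 40 → 80 (Vyndaqel 40 mg, then Vynmac 61 mg) | 80 ⇒ 40 | none |
| 60 → 80 | 80 ⇒ 60 | none |
| 20 → 80 | 80 ⇒ 20 | none |
| 20 → 80 → 60 | 80 ⇒ 20 | 80 ⇒ 60 |
| 80 → 40 → 80 | 80 ⇒ 40 | 80 ⇒ 40 |

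**All possible sequences** of two, three or four doses, with each dose different from the one before it:

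| Doses in sequence | Sequences | Increase only | Of these, filed as a reduction | With a reduction | Of these, filed under a different pair from the largest fall |
|---|---|---|---|---|---|
| 2 | 4×3 = 12 | 6 | 6 | 12 − 6 = 6 | 0 |
| 3 | 4×3×3 = 36 | 4 | 4 | 36 − 4 = 32 | 8 |
| 4 | 4×3×3×3 = 108 | 1 | 1 | 108 − 1 = 107 | 31 |

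Every increase-only sequence is filed as a reduction. These are counts of possible sequences, not expected patient frequencies.

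**Reconciliation with the neighbouring row.** Let R be the number of patients with at least one reduction and U the number whose dose rose and never fell. Within the 20 to 80 mg levels, every patient in R or U has a maximum above the minimum, so the six descending categories sum to R + U. The dose-reduction row shows R. The excess is U, and the two agree only when U = 0.

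**Other text that might supply the order.** The transfer rule at the end of SAP 8.2.2.2 deals only with transferred patients whose overlapping records disagree. It says nothing about the sequence of doses.

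**The case against.** The strongest defence is that the intent is plain. The title refers to reduced doses, the arrow has a direction, every pair descends, and the item follows the reduction and increase rows. A programmer might well code falls over time. The rule also carries an asterisk after the observation period, and the only single-asterisk note visible in the section belongs to the dose-reduction row. That may tie the breakdown to reductions, or a separate note may have been lost when the document was converted.

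This shows intent but supplies neither a time order nor a restriction. The text names the two ends of the arrow as maximum and minimum. The no-change category implies that patients without a reduction are in the table. Even if entry were limited to patients with a reduction, 20 → 80 → 60 mg would still be filed as 80 ⇒ 20 mg, a fall that did not happen.

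The defence is right about importance. A reader might infer three stronger things that the documents do not support:

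- That the plan's tolerability information by dose rests on this table. It does not: SAP 8.2.3.1.3 tabulates adverse reactions by action taken, with reductions and increases kept apart, and SAP section 9 lists patients whose adverse reactions led to dose reduction.
- That the counts of patients with reductions and increases are themselves wrong. They are not defined by maximum and minimum, and they stand.
- That reductions will be overstated by some definite factor, or that the totals must disagree. The documents give no number of dose increases. Protocol 8.2.1 gives 80 mg as the usual Vyndaqel dose, so increases may be few.

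Nor does anything else depend on the table. SAP 5.4 has no dose-change subgroup, SAP section 6 has no dose-change endpoint, and SAP section 4 calls the study non-confirmatory.

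**Conclusion.** The point holds as a fault in a stated rule. Read literally, the rule files every increase-only patient as a reduction and can give a patient with both rises and falls a larger reduction than occurred. The changed categories can exceed the dose-reduction row by the number of increase-only patients.

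The damage is limited to one descriptive table. The table is still worth correcting, because it is the only planned one that shows how large the reductions were. The number of misfiled patients cannot be derived from the documents, and it is zero if no dose rises during observation. The conclusion assumes that the rule is programmed as written and that the asterisk does not point to a missing note that sets the order.

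**What to change.** In SAP 8.2.2.2:

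1. Define the pattern in time order, for example the recorded dose before the first reduction ⇒ the lowest recorded dose after it. Other ordered definitions, such as the largest fall, would also do and can differ when a patient has several changes. The SAP should name one.
2. Give reduction categories only to patients counted in the dose-reduction row, and show all others as having no reduction. The categories then sum to that row.
3. Resolve the asterisk on the observation period.

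A separate ordered table of increases is optional.

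The cost is a sentence or two in the SAP and a small programming change. Protocol 8.3.2 already collects the drug name, daily dose, treatment period and reason for change, so no new data are needed. Only a reporting definition changes; no dosing rule is affected.
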